9.3 Variables

9.3.1 Outcome Assessment

Primary Objective

- Impairment is defined as any of the following:
 - o Neuropsychomotor development impairment in the areas of:
 - Social and emotional
 - Language/communication
 - Cognitive (learning, thinking, problem-solving)
 - Motor (both gross and fine motor development)
 - As lower scores on adaptive functioning measures indicate greater deficits (ie, lower day-to-day functioning), impairment will be defined as performance falling 2 or more standard deviations below the normative population mean in 1 or more adaptive functioning domain(s) (ie, motor, language, social skills).

- As higher scores on executive function (ie, cognitive) measures indicate greater deficits (ie, more problematic thinking), impairment will be defined as performance falling 2 or more standard deviations above the normative population meant in 1 or more executive function domain(s). For motor skills of patients ages 10 years and older, impairment will be defined as having an age-equivalency a year or more below their chronological age, as further development is not expected beyond that age and normative data is limited.
- Individual change over time across domains will also be assessed for significance. Specifically, it is anticipated that patients will have their own respective baseline level of skills across assessed areas. For example, some individuals may have significantly above average day-to-day functioning and/or cognitive skills at the start of the study. Thus, the formal definition of psychomotor 'impairment,' placing two or more standard deviations below the mean, will not capture meaningful changes amongst these patients. To account for this, analysis will also examine statistically significant changes over time within each person's own scores across psychomotor domains. Changes that are two or more standard deviations from one's own baseline will be considered relevant adverse effects.

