9.6 Data Management

All data will be entered by sites into an eCRF that will be used to build the study database. Data abstraction will be done approximately every 6 months $(\pm 30 \text{ days})$ starting from enrolment. Additional data on neuropsychomotor development will be assessed through specific questionnaires (paper and/or electronic) which will be administered at pre-specified intervals starting at enrolment (approximately every 6 months [± 30 days] for patients up to 6 years old and approximately yearly [± 60 days] for patients from 6 years old) either in person or via telephone interview or mail. The score and percentiles from the questionnaires will be used for the final analysis. The final analysis cohort will be constructed from the complete review of inputted data documenting events in a patient's history from primary disease diagnosis until the earliest occurrence of the following events: death, withdrawal of consent, end of available data in the chart, completion of the 12-year follow-up period, or up to the age of 25 years. Data to be abstracted include variables relating to ALL diagnosis, ALL-associated treatment, development impairment, HSCT-associated AEs, leukemia relapse, long-term AEs, secondary malignancy until the earliest of: death, withdrawal of consent, end of available data in the chart, completion of the 12-year follow-up period, or 25 years of age.

Each patient will be assigned a unique identification number at the time of the first data entry. This unique identification number will be used to link data to subsequent data entries. The data will be abstracted by site staff from patient medical records into a web-based electronic data capture (EDC) system, using an electronic abstraction form that will provide an integrated, transparent tool to facilitate and record center recruitment, case identification, patient selection and study progress at the center and patient level.

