9.7.2.2.3 Analysis of the Primary and Secondary Endpoints

Patient incidence proportions (and 95% Cls) for each of the specified outcome events will be summarized. KM estimates for time to first onset of each specified event will be provided.

For the events of interest, events that occur after a relapse or secondary malignancy will be censored as it is unlikely that events that occur after relapsed and treatment for relapse could be considered related to initial chemotherapy or blinatumomab treatment for the prior disease occurrence.

A comparison between the blinatumomab versus chemotherapy group will be conducted at the final follow-up in the study pending adequate sample size is enrolled $(\geq 50 \text{ patients per arm})$ and the blinatumomab and SOC groups are comparable (eg. there is overlap between PS distributions across the two groups, or no critical differences that cannot be accounted/adjusted for). Prior to comparison being conducted, covariates listed in Section 9.3.2 will be evaluated for differences between the two groups. Any covariates that are not comparable between the two (Wald chi-square or t-test, p-value < 0.25), will be evaluated as a covariate for adjustment in the models. The primary and secondary endpoint of discrete events (eg, incidence endpoints) will be compared by a logistic regression which will generate an odds ratio and 95% confidence interval of the odds of developing an event. Endpoints that are time-to-event will be compared by a Cox regression model which will generate hazard ratio and 95% confidence interval for the risk of developing an event. Also, we will additionally conduct a propensity score weighting analysis based on the covariates collected for this study. An additional sensitivity analysis may be done to adjust for the drop-in effect of patients receiving anti-cancer medications during follow-up.

A literature review of published data at the time of the final study report will be performed for the relevant endpoints. If there is any relevant scientific data publicly available by the time when the study ends (> 12 years later), Amgen will provide a comparative analysis. If a sufficient number of patients are identified in publicly available database with information on relevant confounding factors, Amgen will conduct a direct comparative analysis, but descriptive analyses will be undertaken either way.

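### The only between-arm models named for neuropsychomotor development act on yes/no impairment; add a repeated-measures comparison of the Vineland-3 and BRIEF scores, which is more powerful unless the effect is broad and the sample large

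*Protocol*

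**What the plan says.** Section 9.3.1 defines neuropsychomotor impairment as a score at least 2 SD from the normative mean, in the unfavourable direction, in any one adaptive (Vineland-3) or executive-function (BRIEF) domain. Motor skills from age 10 follow a different rule: "impairment will be defined as having an age-equivalency a year or more below their chronological age".

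For children who start well above average, the section says that the formal definition, "placing two or more standard deviations below the mean, will not capture meaningful changes amongst these patients". It therefore adds that "analysis will also examine statistically significant changes over time within each person's own scores across psychomotor domains", and continues: "Changes that are two or more standard deviations from one's own baseline will be considered relevant adverse effects". The questionnaires are repeated every 6 months in the youngest children and yearly from age 6.

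Section 9.7.2 gives continuous variables summary statistics by treatment group. It names logistic or Cox regression for the arm comparison, provided at least 50 patients per arm are enrolled. Section 9.7.2.2.3 says that discrete primary and secondary endpoints "will be compared by a logistic regression which will generate an odds ratio and 95% confidence interval of the odds of developing an event", that time-to-event endpoints go to a Cox model, and that a propensity score weighting analysis will be added. Section 9.6 states: "The score and percentiles from the questionnaires will be used for the final analysis".

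**The concern.** The study collects repeated, norm-referenced scores for up to 12 years, but every comparison model that the protocol names needs a yes/no event or the time to one. Propensity weighting changes the control of confounding, not the outcome scale. The within-child analysis has no between-arm model, and its relevance threshold is again a cut. The statement in section 9.6 that scores will be used therefore has no matching comparison.

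Section 7.2 gives possible harm to the developing brain as a reason for the study, and section 7.3 says the arms will be compared on neuropsychomotor impairment. Under an any-domain, ever-impaired definition, many children in both arms may become cases through ordinary variation. That background can hide a moderate effect, above all one confined to a single domain, even though the scores could show it.

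**Working it through.** **The plan's own figures (section 9.5).** For 98% vs 88% with 52 per arm, the pooled rate is 0.93. The standard error is √(0.93 × 0.07 × 2/52) = 0.0500, so z = 0.10/0.0500 = 2.00 and p = 0.0457 (printed 0.0455). Then 52/0.35 = 148.6, rounded up to 149 per arm and 298 in total. This reproduces. The rates concern having at least one event of any kind, so they say nothing about power for the neuropsychomotor component.

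**Assumptions (mine, not the protocol's).** Normal scores with SD 1; six domains correlated 0.5; 75% of variance stable over time; 12 visits; a constant shift; no dropout, death or censoring at relapse; two-sided 5%. The comparator sits at the norm. The logistic comparison is approximated by a two-proportion z-test. The age-10 motor rule, the own-baseline cut and the Cox model are not modelled.

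**Cut.** Simulating ever being 2 SD or more below the norm in any domain gives these proportions, comparator vs shifted arm:
- 0.5 SD in all domains: 32.2% vs 57.5%
- 0.3 SD in all domains: 32.1% vs 47.1%
- 0.5 SD in one domain: 32.0% vs 38.4%

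Power = Φ[(|p1 − p0| − 1.96·se0)/se1], where se0 is pooled and se1 unpooled. For the first case at 52 per arm: (0.253 − 1.96 × 0.0975)/0.0943 = 0.66, so 74%. Exact enumeration of the z-test gives 78%; I use about 77%. The other two cases give about 36% and 11%.

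**Repeated mean score.** Over six domains and 12 visits the SD is √[(0.5 + 0.5/6)(0.75 + 0.25/12)] = √(0.583 × 0.771) = 0.671. For one domain it is √0.771 = 0.878. Power = Φ[d/(SD·√(2/n)) − 1.96]. At 52 per arm:
- 0.5 SD, all domains: 0.5/0.1315 − 1.96 = 1.84, so 97%
- 0.3 SD, all domains: 0.3/0.1315 − 1.96 = 0.32, so 63%
- 0.5 SD, one domain: 0.5/0.1722 − 1.96 = 0.94, so 83%; with Bonferroni over six domains, 2.904 − 2.638 = 0.27, so 61%

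Allowing for an estimated variance lowers the unadjusted figures by one or two points, to 96%, 61% and 82%.

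| Shift | Cut, 52/arm | Score, 52/arm | Cut, 149/arm | Score, 149/arm |
|---|---|---|---|---|
| 0.5 SD, all domains | about 77% | 96% | 99% | about 100% |
| 0.3 SD, all domains | 36% | 61% | about 76% | 97% |
| 0.5 SD, one domain | 11% | 82% (Bonferroni 61%) | 21% | over 99% (Bonferroni 99%) |

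**Sensitivity.** With the comparator 0.5 SD below the norm, the 0.5 SD results at 52 per arm hardly move: about 72% vs 97% for all domains and 10% vs 83% for one domain.

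**Choice of score.** Averaging all six domains would lose a single-domain effect as well: 0.5/6 = 0.083, and 0.083/0.1315 − 1.96 = −1.33, so 9%. The gain in the last row needs domain-level scores.

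**The case against.** The primary objective is to estimate incidence. That requires a case definition, and logistic or Cox comparison follows naturally from it. This stands, and it is why the incidence comparison should be kept.

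The protocol also plans a within-child change analysis and the use of scores, and an SAP that is not shown may specify a model. A reader might infer that no analysis of scores is planned at all; the text does not support that. What remains is that the protocol fixes a binary outcome and names its comparison models, and none of them can use the scores.

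A reader might also infer that cutting at 2 SD discards most of the power. For one domain at one visit with the comparator at the norm, a 0.5 SD shift at 52 per arm gives 17% vs 71%. But the planned endpoint counts any domain and accumulates over visits, so that figure does not describe it. For a broad 0.5 SD shift the loss is moderate at 52 per arm and negligible at 149.

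Finally, the sentence about missing meaningful changes might be read as an admission of low power. It concerns only children who start above average and is followed directly by a remedy.

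The practical difficulties are real. The protocol itself says motor norms are limited from age 10, the BRIEF form and its indices change with age, and several scores raise multiplicity. They shape the fix but do not remove the need for it.

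**Conclusion.** The point holds as a recommended change. The named arm comparisons use only dichotomised outcomes, which does not fit section 9.6 and gives up information already collected. At 52 per arm the loss is about 19 points for a broad 0.5 SD shift (96 − 77) and 25 points for a broad 0.3 SD shift (61 − 36). For a single-domain 0.5 SD shift it is 71 points unadjusted (82 − 11), or 50 points with Bonferroni (61 − 11). At 149 per arm it is close to nil for the broad 0.5 SD shift and more than 75 points for one domain. These sizes rest entirely on the assumptions listed, because the protocol states no expected score difference. The score comparison was more powerful in every scenario at 52 per arm; how much more depends on how widely the effect spreads.

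**What to change.** Keep the incidence definition and its logistic and Cox comparisons. Add to section 9.7.2.2.3 a pre-specified between-arm comparison of norm-referenced scores by a mixed model for repeated measures. Its terms would be arm, time, arm by time and age at treatment, with the same confounder adjustment or propensity weights as the other comparisons. Report adjusted mean differences in SD units with 95% confidence intervals.

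The paragraph should also:
- name a small set of summary scores, keeping domain-level scores and not only one overall average, and state how multiplicity is handled;
- limit motor scores to ages with adequate norms;
- use a BRIEF composite that is comparable across the preschool, parent and adult informant forms;
- say how scores after relapse or secondary malignancy are treated, since section 9.7.2.2.3 already censors events there.

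The cost is one carefully written paragraph and modest programming, with no new data. The model assumes that missing scores are missing at random, and its results apply to children alive and under follow-up.

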9.3.2 Covariate Assessment

Baseline

- Recording of ALL-related diagnoses history both prior to and following blinatumomab/SOC chemotherapy
 - Disease status (prior to blinatumomab/SOC chemotherapy)
 - MRD status (following treatment; MRD positivity defined at a level $\ge 10^{-4}$ in PCR and/or flow quantification)
 - Relapse (following treatment)
 - Time point of relapse (time since primary diagnosis and time after completion of primary therapy)
 - Whether extramedullary relapse
 - Bone marrow status at relapse
 - Secondary malignancy (following treatment)
- Recording of ALL-related treatment history
 - Details of SOC-chemotherapy therapy
 - Specific therapy
 - Duration of therapy
 - Details of blinatumomab therapy
 - Number of blinatumomab cycles
 - Occurrence of further blinatumomab therapy following initial discontinuation
 - Duration of blinatumomab therapy
- Recording of alloHSCT status
 - Occurrence of alloHSCT
 - Interval between SOC-chemotherapy/blinatumomab and alloHSCT
- Clinically relevant events prior to initiation of therapy or after initiation of therapy and before alloHSCT (see definitions above)
 - Neurological event
 - Endocrine event (including evidence of growth delay)
 - o Immune event
 - Toxicity (gastrointestinal, hematologic, dermatology, cardiac, pulmonary, hepatic, renal, infection, skeletal, etc.: see definitions above)
- Other important clinical factors
 - o Comorbidity
 - Concomitant medication
 - Prenatal development
 - High-risk pregnancy
 - Delivery complications including hypoxia
 - o Gestational time at the delivery
 - APGAR score
 - o Gestational weight (intrauterine growth restriction [IUGR])
 - Psychomotor development impairment and psychiatric conditions recognised prior to the therapy
- Pregnancy and breastfeeding status after blinatumomab initiation

Follow-up

- Demographics and clinical characteristics including comorbidity
 - All treatments for ALL
 - Pregnancy and breastfeeding status

- Recording of further ALL-related treatment history
 - Details of SOC-chemotherapy therapy: specific therapy, and; duration of therapy
 - Details of blinatumomab therapy: number of cycles; occurrence of further blinatumomab therapy following initial discontinuation, and; duration of therapy
- Further HSCT
 - Occurrence of HSCT
 - o Interval between SOC-chemotherapy/blinatumomab and HSCT
 - Outcome of HSCT: early/late GvHD; infection; HSCT-related toxicity (see definitions above)

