The most serious adverse reactions that may occur during blinatumomab treatment include: infections (24.8%), neurologic events (13.8%), neutropenia/febrile neutropenia (10.1%), cytokine release syndrome (3.3%), and tumour lysis syndrome (0.7%). The most common adverse reactions were: pyrexia (69.2%), infusion-related reactions (43.4%), infections – pathogen unspecified (42.1%), headache (32.9%), anaemia (22.8%), thrombocytopenia (20.9%), febrile neutropenia (20.2%), oedema (20.0%), neutropenia (19.7%), rash (16.7%), increased liver hepatic enzymes (16.1%), backerial infectious disorders (15.4%), tremor (15.2%), cough (15.1%), leukopenia (13.4%), back pain (13.3%), chills (13.0%), hypotension (12.8%), viral infectious disorders (12.7%), decreased immunoglobulins (12.5%), cytokine release syndrome (11.6%), tachycardia (11.3%), insomnia (10.7%), fungal infectious disorders (10.6%), and pain in extremity (10.2%).

Amgen is currently assessing long-term safety, efficacy, and survival status in the Study 20120215: a randomized, open-label, controlled phase 3 trial to investigate the efficacy, safety, and tolerability of blinatumomab as consolidation therapy versus conventional consolidation chemotherapy in paediatric patients with B-precursor ALL.

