The 3 major toxicities of blinatumomab are cytokine release syndrome (CRS), neurologic events, and infections. CRS has been observed in the R/R ALL indication in patients with high tumor burden at the start of blinatumomab treatment. CRS is generally an immediate event occurring upon initiating T cell therapy. Similarly, neurologic events are most frequently observed at the beginning of treatment and most clinically resolve, however, the exact mechanism of neurotoxicity is not well defined and the impact, particularly on children younger than two years, is unknown. The blood-brain barrier mechanism in infant is still immature or "leaky", rendering the developing brain more vulnerable to drugs, cytokines and other pathological conditions which could contribute to cerebral damage and neurological disorders. It is totally unknown if blinatumomab crosses the blood brain barrier and to which extent in infants; and what would be the consequence of its passage to the developing brain. Only 10 children under 2 years participated in the pivotal Study MT103-205 and no more than 20 children were of age between 2-6 years where neurotoxicity could also significantly and irrevocably alter brain functioning in the future.

Long term effect of impact of blinatumomab-mediated T-cell activation and its attack on CD-19-positive B cells including normal and malignant B-cells, in particular when considering developing immune system in children, is also unknown and needs to be observed, including an effect of vaccination with live vaccines.

Endocrine complications are among the most common chronic health conditions encountered following haemopoietic stem cell transplant (HSCT) and include thyroid dysfunction, osteoporosis, metabolic syndrome, growth impairment and gonadal dysfunction. The risk of these complications is influenced by pre-HSCT therapeutic exposures, transplantation-related conditioning and post-transplantation management of GvHD. The effect of blinatumomab on the endocrine system, notably followed by HSCT, needs to be evaluated.

Due to these gaps in knowledge this study is a post authorization safety study (PASS) and is category 1 regulatory commitment to the EMA. The current study will allow long-term real-world clinical data to be collected on relevant outcomes to address these uncertainties.

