7.3 Statistical Inference

The study will compare blinatumomab therapy versus chemotherapy for the occurrence of neuropsychomotor developmental impairment, neurological impairment, endocrine impairment, and immune system impairment.

8. Research Question and Objectives

The overarching aim of this study is to describe and compare the long-term safety profile of B-precursor ALL paediatric patients who have been treated with either blinatumomab or chemotherapy prior to undergoing alloHSCT.

Primary 8.1

Primary Objective					
Objective	Endpoint				
 To estimate incidence of neuropsychomotor developmental impairment, endocrine impairment, neurological impairment, and immune system impairment (including auto-immune disorders and vaccine failure) 	 Impairment defined as any of the following: Neuropsychomotor development impairment in any area of social and emotional, language/communication, cognitive, or motor Neurologic impairment defined as any peripheral nervous system disorders including neuromuscular junction disorders; central nervous system disorders Endocrine impairment defined as any Hypothalamus-Pituitary-Gonadal Axis disorders; Hypothalamus-Pituitary-Adrenal (HPA) Axis disorders; Hypothalamus-Pituitary-Thyroid Axis disorders Immune system impairment defined as any leukopenia (neutropenia and/or lymphopenia); low IgG; low IgM, and; low IgA; autoimmune disorders; vaccination failure 				

8.2	Secondary
•	

• To estimate the incidence of Haemopoietic Stem Cell Transplant (HSCT) related adverse events (AEs)	 HSCT-related AEs defined as any second malignancy; Graft versus Host Disease (GvHD); infection, and/or; relapse
 To estimate the incidence of subsequent relapse of leukemia including in the central nervous system (CNS) 	 Relapse is defined as any of the following: Isolated bone marrow relapse (M3³ in the absence of extramedullary involvement) Combined bone marrow response (M2 or M3 marrow and at any extramedullary manifestation of ALL) Extramedullary relapse (either CNS relapse, testicular relapse, or relapse at other sites⁴)

³ Cytological bone marrow assessment grading: see Appendix F for details
 ⁴ See Appendix F for relapse criteria (including extramedullary relapse)

 To estimate the cumulative incidence of long-term AEs 	 AEs in any of the following organ systems: gastrointestinal, hematologic, dermatology, cardiac, pulmonary, hepatic, renal, neurological, infection, immunology, and skeletal

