9.2.1 Study Period

Enrolment of patients into 20180130 will occur if they meet all eligibility criteria. All eligible patients or their caregivers/legal guardians will be approached to provide informed consent for participation. Once informed consent has been given, and all inclusion/exclusion criteria are met, the patient will be enrolled via interactive response technology (IRT) in the study and data collection will begin. The study will commence at the first data collection of the first site. Patients will be followed for a maximum of a 12-year period or up to the age of 25 years, death, withdrawal of consent, or loss to follow-up, whichever comes first. The study will end when 12 years of follow-up for the last patient (if the patient has not withdrawn consent, been lost to follow-up, or died before the end of the 12 years of follow-up) is completed. If the last patient enrolled on study dies or is lost to follow-up before the 12 years following alloHSCT, the remainder

of the patients on study will continue to be followed until all patients on study have reached 12 years following alloHSCT, until death, withdrawal of consent, or lost to follow-up, whichever occurs first.

Data will be entered into an eCRF and will encompass information abstracted from patient charts from routine clinical visits. Data abstraction will be performed approximately every 6 months (± 30 days) starting at enrolment. Additional data on neuropsychomotor development will be assessed through specific questionnaires (paper and/or electronic) which will be administered at pre-specified intervals starting at enrolment (approximately every 6 months [± 30 days] for patients up to 6 years old and approximately yearly [± 60 days] for patients from 6 years old).

The first day of follow-up (day 1) will be the date of successful completion of alloHSCT (following chemotherapy/ blinatumomab treatment).

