9.2.4 Baseline Period

The baseline period will be considered as the time between initial diagnosis of ALL and the alloHSCT. Specific clinical and treatment characteristics will be collected at specific time points during baseline (eg, at diagnosis, prior to SOC/blinatumomab therapy, up to alloHSCT transplant, etc).

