9.4 Data Sources

Specific eCRFs will be designed to collect all the variables needed for this long-term follow-up study. The data in the baseline and follow-up period will be collected through patient questionnaires to be populated by the patient's parents (guardian)/paediatrician (as appropriate) and through medical chart review. Data abstraction from medical chart review will be performed approximately every 6 months (± 30 days) from enrolment. Additional data on neuropsychomotor development will be assessed through specific questionnaires (paper and/or electronic) which will be administered at pre-specified intervals starting at enrolment (approximately every 6 months [± 30 days] for patients up to 6 years old and approximately yearly [± 60 days] for patients from 6 years old) either in person or via telephone interview or mail.

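### Non-ALL drugs that act on the primary endpoints (immunoglobulin replacement, growth factors, systemic immunosuppressants) are not listed for capture after transplant, so treated values and treatment-induced events cannot be recognised

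*Protocol*

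**What the plan says.** Section 9.3.2 splits the covariates into Baseline and Follow-up. "Concomitant medication" appears only under Baseline, among other important clinical factors. Section 9.2.4 fixes that window: "The baseline period will be considered as the time between initial diagnosis of ALL and the alloHSCT". Section 9.2.1 starts the outcome clock at the same point: "The first day of follow-up (day 1) will be the date of successful completion of alloHSCT".

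The Follow-up list in 9.3.2 has demographics and clinical characteristics including comorbidity, "All treatments for ALL", pregnancy and breastfeeding, further chemotherapy or blinatumomab, and further HSCT. Section 9.2.5 likewise speaks of ALL treatments for this period, and the list of data to be abstracted in 9.6 has ALL-associated treatment but no other medication.

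The immune part of the primary endpoint (section 8.1, repeated in 9.3.1) reads: "Immune system impairment defined as any leukopenia (neutropenia and/or lymphopenia); low IgG; low IgM, and; low IgA; autoimmune disorders; vaccination failure". HPA-axis disorders are part of the endocrine endpoint. No text says how a value obtained under replacement or growth factor is classified. Section 9.4 gives the collection route: "Data abstraction from medical chart review will be performed approximately every 6 months (± 30 days) from enrolment".

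Section 7.2 says that the risk of endocrine complications after transplant is "influenced by pre-HSCT therapeutic exposures, transplantation-related conditioning and post-transplantation management of GvHD".

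**The concern.** Listed medication capture stops on the day outcome counting starts. The drugs at issue act on the endpoint itself. Immunoglobulin replacement raises IgG and can disturb vaccine serology. Growth factor raises neutrophils. Systemic steroids and other immunosuppressants can suppress the HPA axis, lower lymphocytes and blunt vaccine response. These are clinical premises; the protocol gives no figures for them.

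Two errors in opposite directions follow. A patient whose IgG or neutrophil count is normal only under support cannot be told apart from one who is truly normal. An endocrine or immune event caused by immunosuppression for GvHD cannot be told apart from a late effect of the leukaemia treatment under study. If use of these drugs differs between the blinatumomab and chemotherapy groups, both errors bias the comparison.

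Section 7.2 gives the effect of B-cell attack on the developing immune system and the endocrine effect of blinatumomab followed by HSCT as reasons for the study. Section 7.1.3 lists decreased immunoglobulins at 12.5%. An analysis plan cannot recover exposures that were never abstracted.

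**Working it through.** **Is the gap real?** The passages side by side:

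- Concomitant medication: listed for diagnosis to alloHSCT (9.3.2 Baseline with 9.2.4).
- Primary outcomes: counted from alloHSCT (9.2.1).
- Treatments listed after alloHSCT: for ALL only (9.2.5, 9.3.2 Follow-up, 9.6).
- GvHD: type, grade, organs, symptoms and resolution are collected (9.3.1), but not its treatment.
- Non-ALL treatment after transplant: one item, intravenous antibiotic use, in the long-term AE list (9.3.1). The protocol does list such an item where it wants one.
- Analysis: the only follow-up medication addressed is anti-cancer drop-in, in an optional sensitivity analysis (9.7.2.2.3).

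So the drug classes are not listed, and 7.2 names GvHD management as a driver of endocrine risk without the variable list carrying it.

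**How large could the masking be?** The protocol gives no rate of support use, so what follows is an illustration. It borrows the planning contrast in 9.5 (98% vs 88%, 52 long-term survivors per arm) as a yardstick. That contrast is not specific to the immune endpoint.

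*Plan's own figure.* Pooled two-sided z-test: mean proportion 0.93; SE = √(0.93 × 0.07 × 2/52) = 0.0500; z = 0.10/0.0500 = 1.998; p = 0.0457. Section 9.5 prints 0.0455, so it reproduces apart from rounding.

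*Assumed inputs.* f = share of impaired patients detectable only through IgG or leukocyte counts (range 2% to 25%). g = share of those normalised by support (range 25% to 75%).

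*Equal masking in both arms.* Recorded difference = (0.98 − 0.88) × (1 − f·g).

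| f | g | Recorded difference |
|---|---|---|
| 2% | 50% | 10 × 0.99 = 9.9 points |
| 10% | 50% | 10 × 0.95 = 9.5 points |
| 25% | 75% | 10 × 0.8125 = 8.1 points |

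*Masking only in the 98% arm.* Recorded rate = 0.98 × (1 − f·g), against 88%.

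| f | g | Recorded rate | Difference | p |
|---|---|---|---|---|
| 2% | 50% | 97.02% | 9.0 points | 0.081 |
| 10% | 50% | 93.10% | 5.1 points | 0.37 |
| 25% | 50% | 85.75% | −2.25 points | 0.73 |

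The first row should not be over-read. It amounts to 52 × 0.98 × 0.01 ≈ 0.5 patient, and p crosses 0.05 because the planning contrast already sits at the threshold. The general result is that even masking does little and strongly one-sided masking can do much. Without the exposure data nobody can tell which applies.

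No calculation is offered for events induced by immunosuppression. The documents give no basis for one.

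**The case against.** The strongest reply is that the immune endpoint is robust by construction. Any one component meets it, so a B-cell deficit can still register through low IgM, low IgA, autoimmune disorder or vaccination failure. Section 9.7.2.2.3 analyses incidence and time to first onset, so a low value recorded after day 1 but before support starts already counts, and later normal values do not undo it. This stands. Full masking needs a patient with no other component who is supported before any low value is seen after transplant. A reader might infer that the B-cell signal is hidden or that its sign would reverse. The documents do not support that: the reversal above needs 25% of impaired patients to depend on IgG or counts alone, and half of those masked in one arm only.

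A reader might also infer that the endpoint is decided by laboratory values alone. The protocol gives no cut-off and does not say whether a measured value or a charted diagnosis decides.

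Three further defences carry less weight. The abstract lists concomitant medication without a period, but in a block with prenatal development and APGAR score, which 9.3.2 places at baseline, and 9.7.2.2.3 points to 9.3.2 for covariates. The contingency form in Appendix C has a concomitant-medication block, but it is event-triggered, and 11.2 ties safety collection to blinatumomab exposure; it is neither systematic nor balanced across arms. GvHD grade and the possible acute-GvHD subgroup in 9.7.2.2.4 are usable partial markers, but they do not show who received immunosuppression or when.

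First-onset analysis and the any-of rule give no protection against events that immunosuppression itself causes. Derivation rules and cut-offs may be left to an analysis plan; the list of collected variables may not.

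**Conclusion.** The point holds as a gap in the protocol's own variable list. Post-transplant immunoglobulin replacement, growth factors and systemic immunosuppressants are not listed for capture, while primary outcomes on which they act are counted over the same period. The low-IgG and leukopenia components may be under-counted, and treatment-induced endocrine or immune events cannot be identified from the listed variables. Whether this biases the comparison depends on use differing between arms, on which the documents are silent.

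The size is unknown. For the immune composite it is limited: on the assumed inputs a 10-point difference stays between 9.9 and 8.1 points in the equal-masking cases shown. It is larger if masking is one-sided. It matters more for the low-IgG and leukopenia components read separately, and for endocrine impairment, where 7.2 already names the missing exposure. This does not invalidate the study. It is a low-cost correction to a safety study with up to 12 years of follow-up.

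**What to change.** 1. In 9.3.2 Follow-up, add start date, stop date and recorded reason for immunoglobulin replacement, growth factors, systemic corticosteroids and other systemic immunosuppressants, taken from the charts already abstracted every 6 months. Align 9.2.5 and 9.6.
2. In 9.3.1, state that IgG values or vaccine titres obtained on replacement, and neutrophil counts obtained on growth factor, are flagged and not taken as evidence of no impairment.
3. As sensitivity analyses, report endocrine and immune impairment with and without concurrent systemic immunosuppression, and low IgG with and without counting replacement given for recorded hypogammaglobulinaemia as impairment. Counting replacement as impairment in the main analysis would redefine the endpoint, so it belongs here only.

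The cost is a protocol and eCRF amendment, a few chart fields and slightly more abstraction time. Prophylactic replacement must be told apart by the recorded reason. The change is cheapest before the first follow-up abstraction. It alters no patient's treatment.
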